### **13.3 Data and Safety Monitoring Board**

A data and safety monitoring board (DSMB) will be in place, composed of independent experts, to monitor the safety and scientific integrity of the study. The DSMB will periodically review accumulated patient data for safety, study conduct and progress and efficacy, and assess the potential benefits and risks to the patient. The DSMB also can provide recommendations to the sponsor related to the continuation, modification or termination of the study. Details of the roles and responsibilities of the DSMB members are regulated in the DSMB charter.

### **13.4 Good Clinical Practice**

The study will be managed and conducted according to the latest ICH GCP and applicable regulatory requirement(s) (specifically the principles of GCP in ICH topic E6, as laid down by the Commission Directive 2005/28/EC and in accordance with applicable local laws and guidelines). A copy of the ICH guidelines can be found in the ISF.

### 13.5 Essential Documents

The ICH guideline for GCP lists a number of essential GCP documents required prior to, during, and after the conduct of the study. It is the responsibility of the monitor to ensure that the Investigator is always provided with a copy of such documents prepared by the study management, and it is likewise the responsibility of the Investigator to provide the monitor with essential documents prepared by the Investigator or the local EC. A complete list of essential GCP documents can be found in the ISF.

### **13.6 Record Retention**

The Investigator must maintain adequate and accurate records to enable the conduct of the study to be fully documented and the study data to be subsequently verified. These records include, but are not limited to, the identity of all participating patients, all original signed informed consent documents, copies of all eCRFs, safety reporting forms, source documents, and detailed records of treatment disposition and adequate documentation of relevant correspondence.

The records should be retained by the Investigator according to ICH, local regulations, or as specified in the clinical trial agreement (CTA), whichever is longest.

### **13.7 Monitoring/Quality Control**

Monitoring visits will be conducted during the study at regular intervals. Monitoring visits will be conducted to ensure protocol adherence, quality of data, accuracy of entries in the eCRF, drug accountability, compliance with regulatory requirements and continued adequacy of the investigational site and its facilities.

Incorrect or missing entries in the eCRFs will be queried and will be corrected appropriately.

All clinical data will undergo quality control checks prior to clinical database lock. Edit checks will then be performed for appropriate databases as a validation routine using SAS® to check for missing data, data inconsistencies, data ranges, etc. Each eCRF will be reviewed and signed by the PI.

### **13.8 Quality Assurance**

Investigational sites may be audited during or after the study is completed by Sponsor representatives, or regulatory authorities may conduct an inspection. The Investigator(s) will be expected to cooperate with such a visit and to provide assistance and documentation (including all study documentation, and patient source data), as requested.

### **13.9 Insurance and Liability**

Insurance and liability for the study is the responsibility of the sponsor, Afimmune. Patient insurance is taken out for study participants in accordance with legal requirements.

### **13.10 End of Trial**

The end of trial is defined as 'last patient last visit (LPLV)'. LPLV is defined as the date the Investigator reviews the last subject's safety data and determines that no further evaluation is required for the subject to complete the trial.

The study will be prematurely terminated should more than one patient experience a Grade 3 or higher AE on the CTCAE scale in any one category that is determined to be possibly or probably attributable to study drug (excluding evaluation of liver function), or a 2-point worsening of modified m-SOFA score if possibly or probably attributable to study drug.

### **13.11 Confidentiality**

All information obtained during the conduct of the study with respect to the patients' state of health will be regarded as confidential. This is detailed in the written information provided to the patient. An agreement for disclosure of any such information will be obtained in writing and is included in the ICF signed by the patient. The study data shall not be disclosed to a third party without the written consent of the Sponsor.

### **13.12 Report and Publication**

Production of a clinical study report (CSR) in accordance with the ICH guidelines will be the responsibility of the CRO. No information from the study will be published without the prior written consent of the Sponsor.

## 15 APPENDICES

### 15.1 Appendix 1: Flow Chart – Pilot Phase

Visit	Screening/ Visit 1	Baseline/ Visit 2	Day 3/ Visit 3	Day 5/ Visit 4	Day 7/ Visit 5	Day 14/ Visit 6	Day 21/ Visit 7	Day 28/Visit 8/ Early Termination	Day 90/Visit 9/ Follow Up
Day		0	3	5	7	14	21	28	90
Visit Window	N/A	±0 day	±0 day	±0 day	±2 day	±2 day	±2 day	±1 day	±10 days
Informed Consent 	X								
Inclusion/Exclusion	X	X							
Demographics	X								
Patient Randomisation		X							
Medical History	X	X							
Physical Examination	X	X	X	X	X	X	X	X	X
Vital Signs	X	X	X	X	X	X	X	X	X
ECG (6-lead or 12-lead)	X	X						X	
Pharmacokinetic Sampling 		X	X	X	X	X	X	X	
Exploratory Blood Sample		X				X		X	
Clinical Laboratory Tests 	X	X	X	X	X	X	X	X	X
Virology	X								
Urinalysis	X								
Liver ultrasound	X								
Pregnancy Test 	X	X				X		X	
MELD	X	X	X	X	X	X	X	X	X
MDF	X	X	X	X	X	X	X	X	X
m-SOFA		X	X	X	X	X	X	X	X
West Haven Criteria	X	X	X	X	X	X	X	X	X
APACHE II		X	X	X	X	X	X	X	X
Lille score		X	X	X	X	X	X	X	X
Total Bilirubin	X	X	X	X	X	X	X	X	X
CK-18		X	X	X	X	X	X	X	X
ALT, AST	X	X	X	X	X	X	X	X	X
Child Pugh Score		X	X	X	X	X	X	X	X
Gamma GT		X	X	X	X	X	X	X	X
Assessment of nutritional status		X				X		X	
Collection of acute kidney injury, ascites and variceal haemorrhage data		X	X	X	X	X	X	X	
Biomarker		x	x	x	x	x	x	x	

Visit	Screening/ Visit 1	Baseline/ Visit 2	Day 3/ Visit 3	Day 5/ Visit 4	Day 7/ Visit 5	Day 14/ Visit 6	Day 21/ Visit 7	Day 28/Visit 8/ Early Termination	Day 90/Visit 9/ Follow Up
Mortality			X	X	X	X	X	X	X
IMP/Placebo Administration		X -----				X			
AE Assessment		X	X	X	X	X	X	X	
Concomitant Medication Assessment	X	X	X	X	X	X	X	X	

 Includes biochemistry, haematology, and coagulation tests. Caeruloplasmin will be collected at screening only

 Female Patients of child bearing potential only.

 Patient may be required to reconsent after Visit 1 if new information is made available.

 PK sampling for pilot phase will be conducted at the following timepoints on Day 0 and Day 7: 0.5hours, 1 hour, 2 hours, 3 hours, 4 hours, 6 hours, 7 hours, 8 hours, 10 hours and 12 hours (before next dose). Trough plasma samples will also be obtained prior to the first daily dose on the indicated days.

## 15. 2 Appendix 2: Study Flowchart – Double-Blind Phase

Visit	Screening/ Visit 1	Baseline/ Visit 2	Day 3/ Visit 3	Day 5/ Visit 4	Day 7/ Visit 5	Day 14/ Visit 6	Day 21/ Visit 7	Day 28/Visit 8/ Early Termination	Day 90/Visit 9/ Follow Up
Day		0	3	5	7	14	21	28	90
Visit Window	N/A	±0 day	±0 day	±0 day	±2 day	±2 day	±2 day	±1 day	±10 days
Informed Consent 	X								
Inclusion/Exclusion	X	X							
Demographics	X								
Patient Randomisation		X							
Medical History	X	X							
Physical Examination	X	X	X	X	X	X	X	X	X
Vital Signs	X	X	X	X	X	X	X	X	X
ECG (6-lead or 12-lead)	X	X							X
Pharmacokinetic Sampling 		X	X	X	X	X	X	X	
Exploratory Blood Sample		X				X		X	
Clinical Laboratory Tests 	X	X	X	X	X	X	X	X	X
Virology	X								
Urinalysis	x								
Liver ultrasound	X								
Pregnancy Test 	X	X				X		X	
MELD	X	X	X	X	X	X	X	X	X
MDF	X	X	X	X	X	X	X	X	X
m-SOFA		X	X	X	X	X	X	X	X
West Haven Criteria	X	X	X	X	X	X	X	X	X
APACHE II		X	X	X	X	X	X	X	X
Lille score		X	X	X	X	X	X	X	X
Total Bilirubin	X	X	X	X	X	X	X	X	X
CK-18		X	X	X	X	X	X	X	X
ALT, AST	X	X	X	X	X	X	X	X	X
Child Pugh Score		X	X	X	X	X	X	X	X
Gamma GT		X	X	X	X	X	X	X	X
Assessment of nutritional status		X				X		X	
Collection of acute kidney injury, ascites and variceal haemorrhage data		X	X	X	X	X	X	X	
Biomarker		x	x	x	x	x	x	x	

Visit	Screening/ Visit 1	Baseline/ Visit 2	Day 3/ Visit 3	Day 5/ Visit 4	Day 7/ Visit 5	Day 14/ Visit 6	Day 21/ Visit 7	Day 28/Visit 8/ Early Termination	Day 90/Visit 9/ Follow Up
Mortality			X	X	X	X	X	X	X
IMP/Placebo Administration		X -----X							
AE Assessment		X	X	X	X	X	X	X	
Concomitant Medication Assessment	X	X	X	X	X	X	X	X	

 Includes biochemistry, haematology, and coagulation tests. Caeruloplasmin will be collected at screening only

 Female Patients of child bearing potential only.

 Patient may be required to reconsent after Visit 1 if new information is made available.

 Trough plasma PK samples will also be obtained prior to the first daily dose on the indicated days.

## 15.2 Appendix 3: Acute Physiologic and Chronic Health Evaluation II

Physiologic Variable	High Abnormal Range					Low Abnormal Range					Points
	+4	+3	+2	+1	0	+1	+2	+3	+4		
Temperature - rectal (°C)	≥41°	39 to 40.9°		38.5 to 38.9°	36 to 38.4°	34 to 35.9°	32 to 33.9°	30 to 31.9°	≤29.9°		
Mean Arterial Pressure - mm Hg	>160	130 to 159	110 to 129		70 to 109		50 to 69		<49		
Heart Rate (ventricular response)	≥180	140 to 179	110 to 139		70 to 109		55 to 69	40 to 54	≤39		
Respiratory Rate (non-ventilated or ventilated)	≥50	35 to 49		25 to 34	12 to 24	10 to 11	6 to 9		≤5		
Oxygenation: A-aDO 2 or PaO 2 (mm Hg)	≥500	350 to 499	200 to 349		<200						
a. FIO 2 ≥0.5 record A-aDO 2					PO2>70	PO2 61 to 70		PO2 55 to 60	PO2<55		
b. FIO 2 <0.5 record PaO 2											
Arterial pH (preferred)	≥7.7	7.6 to 7.69		7.5 to 7.59	7.33 to 7.49		7.25 to 7.32	7.15 to 7.24	<7.15		
Serum HCO 3 (venous mEq/l) (not preferred, but may use if no ABGs)	≥52	41 to 51.9		32 to 40.9	22 to 31.9		18 to 21.9	15 to 17.9	<15		
Serum Sodium (mEq/l)	≥180	160 to 179	155 to 159	150 to 154	130 to 149		120 to 129	111 to 119	≤110		
Serum Potassium (mEq/l)	≥7	6 to 6.9		5.5 to 5.9	3.5 to 5.4	3 to 3.4	2.5 to 2.9		<2.5		
Serum Creatinine (mg/dl)	≥3.5	2 to 3.4	1.5 to 1.9		0.6 to 1.4		<0.6				
Double point score for acute renal failure											
Hematocrit (%)	≥60		50 to 59.9	46 to 49.9	30 to 45.9		20 to 29.9		<20		
White Blood Count (total/mm  ) (in 1000s)	≥40		20 to 39.9	15 to 19.9	3 to 14.9		1 to 2.9		<1		
Glasgow Coma Score (GCS)											
Score = 15 minus actual GCS											
A. Total Acute Physiology Score (sum of 12 above points)											
B. Age points (years) <44=0; 45 to 54=2; 55 to 64=3; 65 to 74=5; >75=6											
C. Chronic Health Points (see below)											
Total APACHE II Score (add together the points from A+B+C)											

Chronic Health Points: If the patient has a history of severe organ system insufficiency or is immunocompromised as defined below, assign points as follows:

5 points for nonoperative or emergency postoperative patients

2 points for elective postoperative patients

**Definitions:** organ insufficiency or immunocompromised state must have been evident **prior** to this hospital admission and conform to the following criteria:

- **Liver** – biopsy proven cirrhosis and documented portal hypertension; episodes of past upper GI bleeding attributed to portal hypertension; or prior episodes of hepatic failure/encephalopathy/coma.
- **Cardiovascular** – New York Heart Association Class IV.
- **Respiratory** – Chronic restrictive, obstructive, or vascular disease resulting in severe exercise restriction (i.e., unable to climb stairs or perform household duties; or documented chronic hypoxia, hypercapnia, secondary polycythaemia, severe pulmonary hypertension (>40 mmHg), or respirator dependency.
- **Renal** – receiving chronic dialysis.
- **Immunocompromised** – the patient has received therapy that suppresses resistance to infection (e.g., immunosuppression, chemotherapy, radiation, long term or recent high dose steroids, or has a disease that is sufficiently advanced to suppress resistance to infection, e.g., leukaemia, lymphoma, AIDS).

Kel	Apparent first-order terminal elimination rate constant
λ _z	Terminal Elimination Rate Constant
LLOQ	Lower Limit of Quantification
LS	Least Squares
MAR	Missing at Random
MDF	Maddrey Discriminant Function
MedDRA	Medical Dictionary for Regulatory Activities

MELD	Model End-stage Liver Disease
MMRM	Mixed-Model Repeated Measures
m-SOFA	Modified Sequential Organ Failure Assessment
NASH	Non-Alcoholic Steatohepatitis
NCS	Not Clinically Significant
%Extrap	Percentage of AUC _{inf} obtained by extrapolation
PK	Pharmacokinetic
PKAP	Pharmacokinetic data analysis plan
PPS	Per Protocol Set
PT	Preferred Term
Q1	25 th percentile
Q3	75 th percentile
R _{ac}	Accumulation ratio at pharmacokinetic steady-state
RAN	All Randomised Patients
SAE	Serious Adverse Event
SAF	Safety Analysis Set
SAP	Statistical Analysis Plan
SD	Standard Deviation
SOC	System Organ Class
SOP	Standard Operating Procedure
SUSAR	Suspected Unexpected Serious Adverse Reaction
t _{1/2}	Terminal Elimination Half-Life
TEAE	Treatment Emergent Adverse Event
t _{max}	Time of the Maximum Observed Plasma Concentration
T _{ss}	Time to achieve pharmacokinetic steady-state
WHO Drug	World Health Organization Drug Dictionary

1 INTRODUCTION

This document details the statistical analysis of the data that will be performed for the Afimmune study: A Randomised, Double-Blind, Placebo-Controlled, Phase II Study to Assess the Efficacy and Safety of Orally Administered DS102 in Patients with Severe Acute Decompensated Alcoholic Hepatitis.

The proposed analysis is based on the contents of Version 4.0 of the protocol (dated 01-AUG-2018). In the event of future amendments to the protocol, this statistical analysis plan (SAP) may be modified to account for changes relevant to the statistical analysis.

The table, listing and figure shells are supplied in a separate document.

2 STUDY OBJECTIVES AND DESIGN

2.1 Study Objectives

Efficacy Objective:

- To compare the efficacy of orally administered DS102 versus placebo, in the treatment of adult patients with severe acute decompensated Alcoholic Hepatitis (AH).

Safety Objective:

- To compare the safety of orally administered DS102 versus placebo, in the treatment of adult patients with severe acute decompensated AH.

Pharmacokinetic Objective:

- To evaluate the pharmacokinetics (PK) of 15(S)-HEPE following orally administered DS102 capsules, in six adult patients with AH in an initial pilot phase of the study, followed by trough level assessment of 15(S)-HEPE in all study participants.

2.2 Study Endpoints

The primary endpoint of the study is:

- Percentage change in Model End-stage Liver Disease (MELD) score from baseline to Day 28.

The secondary endpoints are:

- Change in total bilirubin from baseline to Day 7, 14, 21 and 28
- Proportion of patients showing a 25% reduction of bilirubin at day 7, 14, 21, and 28
- Change in serum Cytokeratin 18-M30/M65 from baseline to Day 7, 14, 21 and 28
- Change in Aspartate Transaminase (AST) levels from Baseline to Day 7, 14, 21 and 28
- Change in AST: Alanine Transaminase (ALT) ratio from Baseline to Day 7, 14, 21, 28
- Change in Maddrey Discriminant Function (MDF) score from baseline to Day 7, 14, 21 and 28

- Proportion of patients showing a 25% reduction in MELD score from baseline to Day 7, 14 and 21
- Change in MELD score from baseline to Day 7, 14 and 21
- Change in modified sequential organ failure assessment (m-SOFA) from baseline to Day 7, 14, 21 and 28
- Proportion of patients with a 2-point worsening of m-SOFA from baseline at Day 7, 14, 21 and 28
- Change in hepatic encephalopathy as assessed by West Haven criteria, from baseline at Day 7, 14, 21 and 28
- Incidence of acute kidney injury over 28 days (defined by requiring medicinal or mechanical support)
- Incidence of variceal haemorrhage, ascites or hepatic encephalopathy over 28 days

The exploratory endpoints are:

- Survival at day 7, 14, 21, 28 and 90 using Kaplan-Meier Plot
- Change in Gamma Glutamyl Transferase (GT) from baseline to Day 7, 14, 21 and 28
- Change in ALT from baseline to Day 7, 14, 21 and 28.
- Change in Child-Pugh score from baseline to Day 7, 14, 21 and 28
- Change in Acute Physiologic and Chronic Health Evaluation (APACHE) II score from baseline to Day 7, 14, 21 and 28
- Change in Lille score from baseline to Day 7, 14, 21 and 28

The safety endpoints are:

- Treatment emergent serious adverse events (SAEs), adverse events (AEs) and suspected unexpected serious adverse reactions (SUSARs)

2.3 Study Design

This is a randomised, placebo-controlled, double-blind, parallel group, multicentre, exploratory phase II study preceded by an open label pilot phase to investigate the efficacy and safety of orally administered DS102 capsules in patients with acute decompensated AH aged over 18 years. Patients will be recruited from 50 sites across 9 countries.

The open label pilot phase is a single arm study, all 6 patients will receive study drug (2 x DS102 500mg capsules orally administered twice a day (BD) (four capsules daily)), for 28 days. Results of the pilot phase will be assessed by a data and safety monitoring board (DSMB) for safety and if dose adjustments for the main study are needed.

After the open-label pilot phase of the study, two parallel groups of patients will be enrolled into the randomised double-blind phase of the study to compare one dose of DS102 with placebo over a 28-day treatment period. Patients will receive standard of care therapy in addition to their assigned investigational medicinal product (IMP)

throughout the treatment period of the study. It is planned that 120 evaluable patients, 60 per treatment group, will be randomised.

The study population will consist of male and female patients diagnosed with severe acute decompensated AH aged 18 years and over.

2.4 Visit Structure

During the study, 8 visits to the clinic are scheduled after the screening visit (Visit 1): one at the start of the comparative treatment period (Baseline/Visit 2) and six in the comparative treatment period (Visit 3/Day 3, Visit 4/Day 5, Visit 5/Day 7, Visit 6/Day 14, Visit 7/Day 21, Visit 8/Day 28 or Early Termination).

A final safety follow-up visit (Visit 9/Day 90) will be conducted on Day 90.

Both the pilot and main, double-blind, phase will follow the same structure.

Full details of the visit structure and scheduled assessments are detailed in the study protocol section 8 Study Conduct and Appendices 1 and 2.

3 SAMPLE SIZE

To discover an effect size of 0.54 (=Difference in means/standard deviation) in MELD change from baseline with 80% power, 55 patients per group are necessary under ideal assumptions using the t-test for independent samples (alpha=0.05, two-sided).

To take deviations from ideal parametric conditions and drop-outs into account, 60 patients per group will be randomised.

4 RANDOMISATION

For the main, double-blind phase, approximately 120 patients will be randomised into double blind treatment groups in a 1:1 ratio as follows:

- Treatment group A: 2 x placebo 500mg capsules orally administered BD (four capsules daily) for 28 days
- Treatment group B: 2 x DS102 500mg capsules orally administered BD (four capsules daily) for 28 days

5 INTERIM ANALYSIS

An interim analysis may be conducted in the main, double-blind phase once 50% of planned patients have completed their Day 28 assessments. Details of this will be covered in a detailed Interim Analysis Plan in accordance with Sponsor standard operating procedure (SOP) "Interim Analysis of Clinical Studies" and is not covered by this SAP.

6 ANALYSIS PLAN

6.1 General

The decision to proceed to the double-blind phase of this study will be determined by the DSMB following review of the safety and pharmacokinetic data from the pilot phase as detailed in the DSMB charter. No statistical outputs will be produced for the DSMB review as part of this SAP, details of the PK analysis for the pilot study are included in Appendix 1. Patients from the pilot phase will be included in the same listings for the double-blind phase as a separate group. Should the study be discontinued after the pilot phase, the listings described in the sections below will be produced for the pilot phase only.

The summary tables and figures described in the following sections relate to the main, double-blind, study only unless specifically mentioned otherwise.

Summary statistics for continuous variables will consist of number of non-missing observations (n), mean, standard deviation (SD), minimum, 25th percentile (Q1), median, 75th percentile (Q3), and maximum, unless specified otherwise. The precision of these variables is defined in the table, figure and listing shells document.

For categorical variables the number and percentage of patients in each category will be presented, based on the number of non-missing observations apart from disposition of patients, protocol deviations, background and demographic characteristics, prior and concomitant medications/procedures and adverse events where the percentage will be based on the number of patients in the analysis set.

All statistical tests will be performed using a two-tailed 5% overall significance level, unless otherwise stated. The null hypothesis at all times will be that the treatments are equivalent. All comparisons between the treatments will be reported with 95% confidence intervals for the difference.

6.2 Blinded Data Review Meeting

The Sponsor will convene a blinded data review meeting (BDRM) after the data has been cleaned and before the study is unblinded.

The BDRM will make decisions that will include, but will not be limited to:

- the determination of whether protocol violations are 'major' or 'minor', or not a protocol violation at all;
- the allocation of patients to analysis sets;
- changes required to the SAP.

After the BDRM and prior to database lock a SAP amendment will be issued if necessary.

6.3 General Derivations

- Definition of baseline

Baseline is defined as the last non-missing value (including scheduled and unscheduled assessments) prior to the patient receiving study treatment.

- Incomplete dates

For calculation purposes, incomplete dates will be completed using worst case. Further details are detailed in the relevant sections as required.

- Non-numeric values recorded in a numeric field

In the case where a variable is recorded as “>x”, “ $\geq x$ ”, “ $<x$ ” or “ $\leq x$ ” in a numeric field, then for analysis purposes a value of x will be taken. Where a range of values is quoted the midpoint of the range will be taken. For example, if a laboratory safety parameter is reported as being below the limit of quantification or $< x$, the value of the limit will be used in the calculation of summary statistics. The recorded value will be reported in listings.

- Methods for handling withdrawals and missing data

Imputation of any data will be detailed in the relevant sections.

6.4 Analysis Sets

The **Enrolled Set** includes all patients who provided informed consent irrespective of whether they received the study treatment.

The “**All Randomised Patients (RAN)**” consists of all patients who were assigned a randomisation number, irrespective of the treatment they received, if any. If this analysis set coincides with the full analysis set, it will be omitted from the tables and listings.

The **Full Analysis Set (FAS)** includes all randomised patients who receive at least one administration of study treatment. Patients will be analysed according to the treatment they are assigned to at randomisation, irrespective of what treatment they actually received.

The **Per-Protocol Set (PPS)** will be a subset of the Full Analysis Set consisting of those patients who:

1. Complete 80% of the study treatment from baseline to day 28 or early termination visit and do not miss more than 3 consecutive days of dosing (or 6 consecutive doses)
2. Have complete MELD score data at baseline and day 28/early termination visit.
3. Do not have major protocol deviations considered having a serious impact on the efficacy results.

All protocol deviations will be assessed and documented on a case-by-case basis prior to the database lock, and major deviations considered having a serious impact on the efficacy results will lead to the relevant patient being excluded from the set. Major protocol deviations considered having a serious impact on the efficacy results include but are not limited to:

- Patients failing any eligibility criteria.

- Patients with treatment deviation.

Protocol deviations other than those specified above may be identified. These will be identified using programmatic data checking where possible, supported by visual review of the data. These deviations will be categorised as either minor or major prior to database lock, at the BDRM prior to unblinding.

The **Safety Analysis Set** (SAF) consists of all patients who take at least one administration of study treatment. Patients will be analysed according to the treatment actually taken.

Pharmacokinetic (PK) Set (pilot phase) will consist of those patients who have at least one quantifiable post-dose plasma 15(S)-HEPE concentration. Patients will be analysed according to the treatment actually taken. An evaluable profile allows the determination of one or more PK parameters and will be determined at the discretion of the pharmacokineticist. The Pharmacokinetic set will be used for the summaries of all PK data.

The **Pharmacokinetic (PK) Set (double-blind phase)** will consist of those patients who have at least one quantifiable post-dose plasma 15(S)-HEPE concentration. Patients will be analysed according to the treatment actually taken.

The treatment actually taken will assumed to be the treatment randomised to unless otherwise notified by the sponsor at the time of unblinding.

The list of patients included in the SAF, FAS, PPS and PK (pilot phase) and PK (double-blind phase) set will be agreed prior to breaking the blind for blinded studies, once all study data is available. The definitions for the SAF, FAS and PK (pilot phase) and PK (double-blind phase) set are sufficient to determine the patients included within these analysis sets and so do not require listing and agreeing prior to breaking the blind for blinded studies.

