### 7.5.2 Withdrawals from Investigational Product

Discontinuation of investigational product, but continued follow-up visits, including efficacy and safety evaluations. Standard reasons for withdrawing from taking further investigational product, but continuing follow-up visits and safety evaluations may be:

- Unacceptable AEs
- Patient request
- Investigator's discretion
- Intercurrent illness
- Pregnancy

Patients who develop Grade 3 or higher National Cancer Institute Common Terminology Criteria or Adverse Events (NCI-CTCAE), or who experience a 2-point worsening of m-SOFA criteria, that is determined to be possibly or probably attributable to the study drug will be discontinued.

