### 10.3 Duration of Treatment

Patients will take assigned medication for 28 consecutive days.

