6.10 Administration of Study Treatment and Compliance

The number of doses of study treatment administered will be derived as the (total number of study drug capsules dispensed – total number of study drug capsules returned) over all visits.

Patients compliance with treatment will be measured by the information captured on the patient diary card.

Overall treatment compliance will be derived as a percentage as the (number of doses of study treatment recorded as being administered/N) *100.

Where N= the number of times the patient should have received study treatment= (Date of treatment withdrawal or day 28/early termination visit – date of baseline visit + 1) x 2

Number of doses of study treatment administered and overall treatment compliance will be summarised.

Study drug dispensing, study drug return and diary card data will be listed.

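### The per-protocol set has no minimum exposure for patients who leave the study early, and the SAP 6.10 compliance formula does not fit the rule it would feed

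*SAP*

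**What the plan says.** The planned course is fixed in length: "Patients will take assigned medication for 28 consecutive days" (Protocol 10.3), with the active arm taking "2 x DS102 500mg capsules orally administered BD (four capsules daily) for 28 days" (SAP 4).

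SAP 6.4 sets three conditions for the PPS.

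- **Criterion 1:** the patient must "Complete 80% of the study treatment from baseline to day 28 or early termination visit" and must "do not miss more than 3 consecutive days of dosing (or 6 consecutive doses").
- **Criterion 2:** the patient must "Have complete MELD score data at baseline and day 28/early termination visit".
- **Criterion 3:** the patient must have no major deviation seriously affecting efficacy. The open list of such deviations includes "Patients with treatment deviation", which is not defined.

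SAP 6.10 defines a compliance percentage to be summarised. Its denominator N is "Date of treatment withdrawal or day 28/early termination visit – date of baseline visit + 1) x 2" (the opening bracket falls outside the quote). SAP 6.4 does not say whether its 80% is this percentage.

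Protocol 7.5.2 provides for patients who stop drug but stay in the study: "Discontinuation of investigational product, but continued follow-up visits, including efficacy and safety evaluations". SAP 6.11.2 uses the PPS for one of two sensitivity analyses of the primary endpoint; the other carries the last observation forward. Protocol 12.6 calls the PPS supportive.

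**The concern.** An exposure threshold in a per-protocol definition normally ensures that the set received most of the regimen. Here the threshold is relative to the time the patient stayed. Someone who takes the capsules reliably for a few days and then leaves meets it, provided an early-termination MELD is obtained. The gap clause does not help, because such a patient has no gap before leaving.

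The set can therefore hold patients with a small part of the course while excluding completers who took about four fifths of it. Agreement between the PPS and the full analysis set (FAS) would then say less about the 28-day regimen than a reader would expect from an 80% rule. Because 6.4 and 6.10 define the window differently, two programmers could also build different sets from the same data.

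**Working it through.** **Inputs.** Duration is 28 days (Protocol 10.3), with two administrations a day (SAP 4). Both doses are taken on Day 0 (Protocol 8.2.3), and the last dose falls on the day before the Day 28 or early-termination visit (Protocol 10.2). The threshold and gap rule are from SAP 6.4 and N is from SAP 6.10. The plan states no dose count or minimum exposure to reproduce. Its one power figure (55 per group, power 0.8014 at effect size 0.54) does reproduce from the noncentral t distribution, but nothing below depends on it.

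**1. Planned doses.** 28 × 2 = 56, on Days 0 to 27. Of these, 80% is 44.8, so 45 doses.

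**2. Fully adherent Day 5 terminator.** Doses on Days 0–4: 5 × 2 = 10. N = (5 − 0 + 1) × 2 = 12. Compliance is 10/12 = 83%, so criterion 1 is met. Share of the planned course: 10/56 = 18%.

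**3. Minimum qualifying exposure by termination day.** Doses needed = 0.8 × N, rounded up; share = doses/56. The last two columns repeat this without the formula's extra day (N = 2 × day).

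| Terminated on | N (6.10) | Doses needed | Share of 56 | N without +1 | Share of 56 |
|---|---|---|---|---|---|
| Day 5 | 12 | 10 | 17.9% | 10 | 8/56 = 14.3% |
| Day 7 | 16 | 13 | 23.2% | 14 | 12/56 = 21.4% |
| Day 14 | 30 | 24 | 42.9% | 28 | 23/56 = 41.1% |
| Day 21 | 44 | 36 | 64.3% | 42 | 34/56 = 60.7% |

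The absence of a floor therefore does not depend on which count is used. A share below one fifth is possible only for termination by about Day 5 (Day 6 without the extra day).

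**4. Completer under the 6.10 formula.** At Day 28, N = (28 − 0 + 1) × 2 = 58, although 56 doses are planned. Perfect adherence scores 56/58 = 96.6%. The threshold becomes 0.8 × 58 = 46.4, so 47 doses.

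- 45 doses: 45/56 = 80.4% of plan, but 45/58 = 77.6%, excluded.
- 46 doses: 46/56 = 82.1% of plan, but 46/58 = 79.3%, excluded.

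**5. Patient who stops drug on Day 5 but attends Day 28.** This patient has no early-termination visit, so the 6.4 window runs to Day 28. Exposure is 10/56 = 18%, and Days 5–27 (23 consecutive days) are missed. Both parts of criterion 1 fail. Under 6.10 the denominator stops at treatment withdrawal, so the same patient scores 10/12 = 83%. The two sections disagree on the percentage; the gap clause, read over the 6.4 window, keeps the patient out.

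**The case against.** The strongest defence is that a set of patients who were adherent while in the study is a coherent choice. They contribute on-treatment data to the repeated-measures model until they leave. Requiring 45 doses and a Day 28 MELD conditions the set on surviving and tolerating 28 days, in a disease where Protocol 1.1 cites mortality above 30%, and that selection may differ by arm. This stands as a cost of the fix. It does not explain why the SAP uses an 80% rule with no floor, and the SAP does not describe the set in these terms.

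Second, the blinded data review meeting allocates patients to analysis sets (SAP 6.2) and could exclude early leavers as treatment deviations. It could, but nothing requires it, and Protocol 7.5 permits withdrawal without calling it a deviation.

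Third, few patients may be affected. Deaths and losses to follow-up without an early-termination visit fail criterion 2, and patients who only stop drug are meant to remain under follow-up. This also stands; the documents give no early-termination rate.

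A reader might go further and infer two things that the documents do not support.

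- **That patients long off drug at Day 28 enter the PPS under 6.4.** They do not: the window runs to Day 28 and the gap clause excludes them. Only importing the 6.10 cut-off would let them in.
- **That the design effect size of 0.54 can be scaled down by the share of short-exposure patients.** SAP 6.11.1 enters early-termination MELD at the next scheduled visit, not at Day 28. A first-week leaver therefore has no Day 28 value and affects that estimate only through the model. Termination after Day 21 can reach the Day 28 slot, but by Day 21 the minimum qualifying exposure is already 64%.

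**Conclusion.** The point holds as a defect in the PPS definition. Criterion 1 sets no minimum exposure for patients who leave early: 18% of the planned doses is enough for a Day 5 terminator with 10 of 12 doses, and 43% for a Day 14 terminator. If the 6.10 formula supplies the percentage, it also contradicts 6.4 for patients who stop drug but stay in follow-up, and it wrongly fails completers with 45 or 46 of 56 doses.

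This assumes the 28-day twice-daily schedule in SAP 4, an early-termination MELD for the patients concerned, and no discretionary exclusion at the blinded review. The completer miscount further assumes that 6.10 feeds criterion 1, which the SAP neither states nor rules out. The effect on the PPS estimate cannot be sized from the documents. The FAS analysis is unaffected, so this should be settled before unblinding but does not threaten the primary result.

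**What to change.** Amend the SAP before database lock.

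- **6.4, criterion 1:** at least 80% of the 56 planned doses (45 or more) between first dose and Day 28, keeping the existing gap rule over that whole period.
- **6.4, criterion 2:** MELD at baseline and at Day 28, within the visit window.
- **6.10:** keep while-on-treatment compliance as a descriptive summary only. Remove the extra day so that N is 56 for a Day 28 completer. State that the numerator counts administrations (two a day): the section first derives doses from capsule counts, which run at four a day.
- **Interpretation:** state that this PPS is conditional on surviving and staying on treatment, and is supportive only.

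If the sponsor prefers a set of patients adherent while in the study, it should name it as such and not present it as evidence on the 28-day course. The criterion 3 category should then say whether early study termination counts as a treatment deviation.

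No new data are needed. The cost is a smaller PPS, more strongly selected on post-randomisation outcomes.
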